### **Missing Data**

Every attempt will be made to ensure data completeness. We do not anticipate much loss to follow-up because of the relatively short time follow-up interval. Conservatively, we would estimate that fewer than 5% of subjects will drop out/withdraw from the study. The participant will be withdrawn from the study follow-up and procedures if the participant withdraws consent, or the sponsor decides to close the study.

If any, the loss of data would almost certainly be due to the fact that the subjects refused to complete or did not show up for the assessment of PTS 30 days (+/- 3 days) after the baseline assessment on shooting day. If the subjects reschedule the follow-up appointment for a later date for any reason, and if this delay is within 30 days of the scheduled date, the data will be considered valid and used in the efficacy analysis. Any measure outside this time window of +30 days will be defined and considered missing data.

Missing PTS at 30 days will be imputed using SAS PROC MI procedure within each treatment group using the distribution implied by the non-missing data for the specific treatment group.

The SAS code below using MICE via the Fully Conditional Specification (FCS) statement will be used to impute the missing data under the missing at random (MAR) assumption.

```
PROC MI DATA=X SEED=<value> NIMPUTE=10 OUT=MI_OUT1 NOPRINT;
CLASS GROUP;
VAR AGE PTA LSurg.....;
FCS LOGISTIC(PTS);
RUN;
```

The estimates of the analysis of the 10 imputed datasets will be then combined following Rubin's rules using PROC MIANALYZE procedure in SAS which will be of the form:

```
PROC MIANALYZE PARMS=GMPARMS COVB=GMCOVB PARMINFO=GMPINFO WCOV BCOV
TCOV; / *dataset "gmparms" contains the estimates and associated
standard errors for the mean parameters from each of the M=10 imputed
data sets.
dataset "gmcovb" contains the asymptotic covariance matrices
dataset "gmpinfo" contains parameter info*/
  
MODELEFFECTS group;
RUN;
```

### 12.3 Sample size estimation

#### Sample size estimation for primary outcome measure.

Calculation of sample size for this study is based on a balanced design and a one-sided significance level of 0.025. We estimate that among officers identified as being at high risk for permanent hearing loss due to having TTS, the proportion of PTS positive officers 30 days (+/- 3 days) after shooting will be 50%. This is the proportion of PTS positive we expect to observe in the placebo group. Thus, for the primary outcome, we estimated that 66 subjects per group will provide us with 80.5% power to detect a 50% reduction in the proportion of PTS positive officers (from 50% to 25%) at the 1-sided alpha level of 0.025 and with 84% power to detect a 50% reduction in the proportion of PTS positive officers (from 50% to 25%) at the one-sided alpha level of 0.025. Our one-sided hypothesis is supported by animal studies, and lack of any evidence of hearing loss as a side effect of ZNS in human studies. A total of 132 subjects will be enrolled.

Using a number needed to treat estimate for the assumed proportion of officers with PTS positive in each study group, the absolute risk reduction of 25% tells us that we will need to treat 4 officers with TTS with ZNS to protect 1 from PTS. We do not expect to have any missing data in this short-term study, so no plan for missing data analysis is included.

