2.7 Sample Size Determination for The Primary Efficacy Outcome Measure

Calculation of sample size for this study is based on a balanced design and a one-sided significance level of 0.025. We estimate that among officers identified as being at high risk for permanent hearing loss due to having TTS, the proportion of PTS positive officers 30 days (+/- 3 days) after shooting will be 50%. This is the proportion of PTS positive officers we expect to observe in the placebo group. Thus, for the primary outcome, we estimated that 66 officers per group will provide us with 80.5% power to detect a 50% reduction in the proportion of PTS positive officers (from 50% to 25%) at the 1-sided alpha level of 0.025. A planned total of 132 subjects is to be enrolled and randomized.

We will make all the needed efforts to eliminate drop outs, and due to short term-follow-up of the study subjects in a period we do not expect any drop-outs or lost to follow-up.

All sample size calculations were carried out using PROC POWER procedure in SAS 9.4.

3 Study Outcomes

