5.2 Missing Data

Every attempt will be made to ensure data completeness. We do not anticipate much loss to follow-up because of the relatively short time follow-up interval. Conservatively, we would estimate that fewer than 5% of subjects will drop out/withdraw from the study. The participant will be withdrawn from the study follow-up and procedures if the participant withdraws consent, or the sponsor decides to close the study.

Data loss, if any, would almost likely be due to subjects refusing to complete or not returning at all for the post-shooting assessment of PTS 30 days (+/- 3 days). If the subject reschedules the post-shooting appointment for a later date for any reason, and if this delay is within 30 days of the scheduled date, the data will be considered valid and used in the efficacy analysis. Any measure outside this time window of +30 days will be defined and considered as missing data.

Missing PTS at 30 days will be imputed using SAS PROC MI procedure within each treatment group using the distribution implied by the non-missing data for the specific treatment group. The SAS code below using MICE via the Fully Conditional Specification (FCS) statement will be used to impute the missing data under the missing at random (MAR) assumption.

```
PROC MI DATA=X SEED=<value> NIMPUTE=10 OUT=MI_OUT1 NOPRINT;
  CLASS GROUP;
  VAR AGE PTA LSurg....;
  FCS LOGISTIC(PTS);
  RUN;
```

The estimates of the analysis of the 10 imputed datasets will be then combined following Rubin's rules using PROC MIANALYZE procedure in SAS which will be of the form:

```
PROC MIANALYZE PARMs=GMPARMS COVB=GMCOVB PARMINFO=GMPINFO WCOV BCOV
  TCOV; / *dataset "gmparms" contains the estimates and associated standard errors
  for the mean parameters from each of the M=10 imputed data sets.
  dataset "gmcovb" contains the asymptotic covariance matrices
  dataset "gmpinfo" contains parameter info*/
  MODELEFFECTS group;
  RUN;
```

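### The 80.5% power holds only if all 132 officers are assessed; the plan's own loss ceiling gives about 78–79%, and Protocol 12.3 denies a missing-data plan that exists

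*Protocol*

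**What the plan says.** **Sample size.** Protocol 12.3 states: "we estimated that 66 subjects per group will provide us with 80.5% power". The effect in question is a halving of the PTS-positive rate, 50% on placebo against 25% on ZNS, tested one-sided at 0.025. Total enrolment is 132, exactly twice 66. The section then says that no missing data are expected, "so no plan for missing data analysis is included". SAP 2.7 gives the same size and power and adds that "we do not expect any drop-outs or lost to follow-up". It does not repeat the clause about there being no plan.

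**Missing data.** SAP 5.2 reads: "Conservatively, we would estimate that fewer than 5% of subjects will drop out/withdraw from the study". The Missing Data text in Protocol 12.2.2 gives the same estimate ("fewer than 5% of subjects will drop out/withdraw from the study"). Both sections impute missing PTS within treatment group by multiple imputation under a missing-at-random assumption, with sample code. Both also accept a follow-up visit rescheduled by up to 30 days as valid.

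**Sensitivity analyses.** Protocol 12.2.1 and SAP 7.1.1 add two analyses of the primary endpoint based on multiple imputation: one under missing-not-at-random, and a tipping-point analysis.

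**Other power figures.** Protocol 12.3 also gives 84% for the same rates and alpha as the 80.5%. Protocol 12.4 and SAP 9 give 79.4% overall power once the futility look is counted.

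**The concern.** Two statements about the same trial cannot both stand. The sample-size sections expect no loss; the missing-data sections expect some, though less than 5%. Because 132 is 2 × 66 without inflation, any lost outcome takes the trial below the number on which 80.5% was computed.

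The clause in Protocol 12.3 matters separately from the power figure. Someone who reads only that section would conclude that nothing was prespecified for missing primary outcomes, when the same protocol sets out an imputation method and two sensitivity analyses. That is awkward to defend when the results are reported.

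**Working it through.** **Inputs.** Placebo rate 50%, ZNS rate 25%, one-sided alpha 0.025, 66 per group (Protocol 12.3, SAP 2.7); Fisher's exact test (Protocol 12.2.1, SAP 7.1.1); loss below 5% (Protocol 12.2.2, SAP 5.2).

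**Step 1: reproduce the stated figure.** SAP 2.7 names the SAS procedure but not the method. The arcsine approximation with continuity correction for equal arms of size n is

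power = Φ{ [arcsin√(p₁ − 1/2n) − arcsin√(p₂ + 1/2n)] × √(2n) − 1.960 }.

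At n = 66, 1/2n = 0.00758:
- arcsin√0.49242 = 0.77782 and arcsin√0.25758 = 0.53230; difference 0.24552
- 0.24552 × √132 = 2.8208
- 2.8208 − 1.9600 = 0.8608, and Φ(0.8608) = 80.53%

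This matches 80.5%, so the stated figure uses all 66 per arm.

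**Step 2: the largest loss that the plan allows for.** 5% of 132 is 6.6, so fewer than 5% means at most 6 officers (6/132 = 4.5%). Balanced, that is 3 per arm, leaving 63.

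**Step 3: power at 63 per arm.** 1/2n = 0.00794:
- arcsin√0.49206 = 0.77746 and arcsin√0.25794 = 0.53272; difference 0.24475 (before rounding)
- 0.24475 × √126 = 2.7473
- 2.7473 − 1.9600 = 0.7873, and Φ(0.7873) = 78.4%

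**Step 4: the planned test itself.** Exact power sums the binomial probabilities of all outcome pairs for which the one-sided Fisher p-value is at most 0.025.

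| Assessed per arm | Arcsine, corrected | Exact Fisher |
|---|---|---|
| 66 | 80.5% | 81.3% |
| 65 | 79.9% | 80.9% |
| 64 | 79.2% | 80.2% |
| 63 | 78.4% | 79.4% |

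If the 6 losses fall unevenly, the arcsine figure stays at 78.3–78.4%. The exact figure moves between 77.3% (61 placebo, 65 ZNS) and 80.1% (62 placebo, 64 ZNS) because the test is discrete.

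**Step 5: what imputation could add.** Steps 3 and 4 treat a missing outcome as lost information. The planned imputation might recover part of it. The list of imputation variables is left open in the sample code, and neither document says how well they predict PTS. With partial recovery, power lies between the rows for 63 and 66.

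**Step 6: the other stated figures.** For the same inputs, a pooled normal test without continuity correction gives 85.1%, near the 84% in Protocol 12.3. For the futility look, take θ = Φ⁻¹(power) + 1.960 and compute P(Z₁ > 0.5233 and Z₂ > 1.960), where the means are θ√(1/3) and θ and the correlation is √(1/3). Starting from 80.5%, θ = 0.860 + 1.960 = 2.820 and the result is 74.2%; starting from 85.1%, it is 79.1%. This is only a normal approximation, but it suggests that the 79.4% overall power does not share the basis of the 80.5%.

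**The case against.** The best defence is that 80.5% is not a miscalculation. It reproduces, and both sample-size sections say openly that no loss is expected. Fewer than 5% is a ceiling that the plan itself calls conservative, and late visits are accepted for up to 30 days, which should keep actual loss lower. At that ceiling the planned exact test still has 79.4%, so the shortfall from 80.5% is only 1 to 2 points, not much more than the gap between the two methods at full enrolment (80.5% and 81.3%). All of this stands, and it limits the point to a correction of text and reporting.

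It does not rescue the clause in Protocol 12.3, which the same document contradicts. Nor does the 79.4% overall power answer the point: that figure describes the futility look and makes no allowance for missing data.

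Four stronger readings are tempting and not supported:
- **Power is simply 78%.** That is the lower of two ceiling values and depends on imputation recovering little, which is an assumption.
- **The trial needs more officers.** Keeping 66 assessed per arm after a full 5% loss would take 66/0.95 = 69.5, so 70 per arm and 140 in total. Neither document sets a minimum power that a drop of 1 to 2 points would breach.
- **No missing-data method was prespecified.** One was; only Protocol 12.3 says otherwise.
- **The primary result rests on imputation.** The primary test is an unadjusted Fisher test. The missing-data sections say that missing PTS will be imputed, but their pooling code combines model estimates and does not show how Fisher results would be pooled.

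**Conclusion.** The point holds, and it is minor. The clause denying a missing-data plan is wrong as written. The expected loss is zero in Protocol 12.3 and SAP 2.7 but up to just under 5% in Protocol 12.2.2 and SAP 5.2. The 80.5% is correct for complete data only. At 6 lost and 63 assessed per arm, power is 78.4% on the stated figure's own method and 79.4% by exact Fisher.

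These values rest on the planned 50% and 25% rates, balanced loss at the ceiling, loss unrelated to outcome, little information recovered by imputation, and no futility look. Smaller loss or useful imputation brings power closer to the complete-data figures; counting the futility look lowers it.

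**What to change.** 1. In Protocol 12.3, delete the clause saying that no missing-data plan is included, and refer to the Missing Data text in Protocol 12.2.2 and to SAP 5.2.
2. In Protocol 12.3 and SAP 2.7, replace the expectation of no loss with the estimate of fewer than 5% used elsewhere.
3. State power as 80.5% with all 132 assessed and about 78–79% at the 5% ceiling. Say that both are before the futility look and that the lower range assumes little recovery from imputation.
4. In the same edit, reconcile these figures with the 84% in Protocol 12.3 and the 79.4% overall power in Protocol 12.4 and SAP 9, naming the method and the loss assumption behind each. Otherwise the restated 78–79% could fall below a power that already includes stopping for futility, which cannot be so on a common basis.

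The cost is a slightly less favourable stated figure. The number of participants, the design and the tests do not change.

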#### Sample size for secondary outcome measures.

Blioskas et al. reported that 280 out of 344 (81%) military cadets had TTS. Thus, for TTS as secondary outcome measure, the estimated sample size of 63 subjects in each arm will provide us with 96.1% power to detect a 40% reduction in the proportion of subjects experiencing TTS (from 80% to 48%) at the 1-sided alpha level of 0.0235.

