### **3.1b Enrollment Inclusion Criteria**

1. Observed audiometric TTS  $\geq$  10 dB HL at 2, 3, 4 and/or 6 kHz

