#### **4.0 STUDY DESIGN**

A randomized, double-blind, and placebo-controlled clinical trial has been designed.

Study participants will be recruited from the Akron Police Department, Summit County Police Department, and other local surrounding police departments. Police officers will be offered participation if they are training for firearm certification as part of their standard occupational requirements. These are officers that would be recommended and/or required to complete these trainings/certifications despite this investigation and this investigation will have no influence on audiologic recommendations.

The primary efficacy endpoint will be the proportion of PTS-positive subjects defined as the ratio of PTS-positive subjects to total number of subjects within each study arm/group. Subjects defined as PTS-positive will demonstrate an increase in threshold that is  $\geq 10$  dB HL at any frequency from 2-6 kHz post-shooting as compared to baseline audiogram.

The secondary efficacy outcome measures will be: (1) the proportion of PTS-positive subjects as defined above, but the definition of PTS will also include the NIOSH red flag guideline for permanent threshold shift: an increase in hearing threshold level of 15 dB or more at any frequency (2, 3, 4, 6 kHz). (2) The rate of temporary cochlear change as measured by a DPOAE amplitude shift at any frequency that is significantly greater than the stability of each measurement (i.e., 95% confidence interval of each measurement do not overlap). The rate of DPOAE shift is the ratio of DPOAE shift-positive subjects to total subjects within each arm.

Interested police officers will be consented and enrolled in the study. They will then undergo screening for TTS following shooting range noise exposure. Those officers identified with TTS will be randomized via an interactive randomization tool (IRT) and assigned to a study group. Once assigned the subject will be provided a kit that will contain either ZNS (100 mg PO) or a placebo. The ZNS and placebo capsules will look, taste, and smell the same. Participants will be instructed to take zonisamide without food. We will recommend that capsules be swallowed whole per the current approved labeling. Those without TTS will be finished with their study commitment.

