## 5.2 Randomization

Following identification of TTS, eligible participants will be randomized via an interactive randomization tool (IRT) in a balanced fashion into one of two study groups: ZNS (100 mg PO) or placebo. Randomization will be based on a randomization list generated from the study statistician using a computer algorithm written in SAS using randomly selected blocks of sizes 2. Within each block of 2, there will be 1 subject assigned to each study group. To balance noise-exposure history across study arms we will employ stratified randomization. The subjects will be stratified based on noise exposure survey responses (see table below), and will then be randomized to study groups. The random assignment of subjects to the different study groups will be associated with consecutively assigned study identification numbers (Study ID) which will be unique for each study participant. The stratified randomization kit list will be provided to Advanced Rx who will package and label the drug for shipment to the pharmacist for each participant. Each bottle will be labeled with the kit number, study ID, and instructions on how to take the medication. The bottle will not contain any information of the treatment allocation.

- ZNS (100 mg PO) group
- Placebo PO group

Name	Description
1: High Noise	Screening: LENS-Q Adapted for Police Officer

Name	Description
	
1A Or 2A Or 3A =
 
a.Daily, Or b.Less than daily/more than weekly, Or c.Weekly, Or d.Less than weekly/more than monthly Or e.Monthly
 
OR
 
1C Or 2C Or 4C <math>\geq 5</math> Years

2: Low Noise	
Screening: LENS-Q Adapted for Police Officer
 
1A AND 2A AND 3A =
 
f.Less than monthly/more than yearly, g.Yearly, h.Less than yearly Or i.Never
 
OR
 
1C AND 2C AND 4C <math>< 5</math> Years

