## 9.0 STUDY CALENDAR

	VISIT 1 Screening Assessment	VISIT 2 Baseline Assessment	Post-training		
			VISIT 3 Within 5-30 Minutes	VISIT 4 Within 24 Hours	VISIT 5 30 days (+/- 3 days)***
Informed Consent	X				
Demographic Info	X				
Current Meds	X				
Questionnaires	X				X
Cognitive Assessment		X		X	
Clinical ear exam	X	X	X		X
Audiogram	X	X	X		X
ECochG		X			X
DPOAE		X	X		X
WIN		X			X
Sound Measurements	X	X	X		
Randomization			X*		
Oral Dose* ZNS or Placebo			X**		
Blood draw**		X		X	
AE Assessment			X	X	X

\* Dispensed after training if TTS is identified on audiogram 5-30 minutes after shooting.

\*\* Blood draw: Electrolyte panel, BUN, Cr, ALT, and AST; DNA analysis and serum pregnancy test at baseline

\*\*\* If TTS is seen from pure tones after each training session

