For this study, we have approximately 800 officers from Akron and Summit County, not including additional local police departments from which to screen and recruit, understanding a large percentage of the population may already present with significant NIHL, thus, may not meet the eligibility criteria. In a previous study by the investigators, 62-85% of police officers presented with evidence of NIHL (62.5% of canine police handlers and 85.7% of non-canine police handlers), therefore, we need a significantly larger sample size to recruit subjects that meet our eligibility criteria. We estimate that each year we will have at least 60 officers screened within 1 hour of shooting each year. If the rate of TTS after 1 hour of shooting is that of the study from Blioskas et al, we estimate that 48 officers will qualify to undergo randomization each year. If 70% of them consent to be randomized there will be 34 officers enrolled and completing the trial each year. Based on these estimates, we will be able to meet our accrual goals and complete the study with a sample size of 132 officers in approximately 4 years.

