2.5 Treatment Assignment and Blinding

The study will be “masked” or “blinded” in the sense that all the study subjects and the study team members will be blinded to the assignment in the study groups. Only the pharmacist who will prepare the study drug kits and the unblinded statistician will have access to the kit assignments. The Medical Monitor will be contacted. A copy of the randomization list with study ID assignments will be saved in a limited access folder on a secure network server at Pharm-Olam. The Medical Monitor will be contacted in emergent medical cases when knowing the treatments assignment is mandatory for clinical care of the study subject.

The data will be presented without having the treatment assignments of individual study subjects made known to study team members including the study PI. Table shells will be blinded. If DSMB members find any safety issues, they may request specific unblinded data. Table shells for DSMB (content and formats) will be agreed upon prior to start of study.

Subjects will receive one time dose of oral ZNS or matching placebo after training if TTS is identified on audiogram 5-30 minutes after shooting. Subjects will be instructed to take study drug without food. We will recommend that capsules be swallowed whole per the current approved labeling.

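### Protocol 12.3 claims 96.1% power for a between-arm difference in the TTS rate, but TTS is the entry criterion and is established before dosing, so the comparison has no power

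*Protocol*

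**What the plan says.** **Power claim.** The secondary-outcome paragraph of Protocol 12.3 cites TTS in 280 of 344 military cadets (81%). It then states that "for TTS as secondary outcome measure, the estimated sample size of 63 subjects in each arm will provide us with 96.1% power" for a 40% relative reduction, from 80% to 48%, at one-sided alpha 0.0235.

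**Entry and dosing.** The enrollment criterion in Protocol 3.1b is "Observed audiometric TTS" of at least 10 dB at 2, 3, 4 and/or 6 kHz. Protocol 5.2 gives the order: "Following identification of TTS, eligible participants will be randomized via an interactive randomization tool (IRT". Protocol 4.0 adds: "Those without TTS will be finished with their study commitment". The footnote to the calendar in Protocol 9.0 says of the dose: "Dispensed after training if TTS is identified on audiogram 5-30 minutes after shooting". SAP 2.5 agrees: "Subjects will receive one time dose of oral ZNS or matching placebo after training if TTS is identified on audiogram 5-30 minutes after shooting".

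**Accrual.** Protocol 12.4 applies the TTS rate from the same cited study to 60 officers screened per year: "we estimate that 48 officers will qualify to undergo randomization each year".

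**Outcome lists.** Protocol 12.2.2 and SAP 7.1.2 name Audiometric TTS among the secondary outcomes, and both use average post-shooting TTS as a covariate in the ANCOVA. Protocol 2.2, Protocol 4.0 and SAP 3.3 list no TTS outcome, and SAP 2.7 contains no TTS power statement. Protocol 4.0 does list a rate of temporary cochlear change measured by DPOAE, without naming a visit.

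**The concern.** A power statement for a between-arm comparison presumes an outcome that can differ between arms because of treatment. Here the stated outcome is the condition for being randomised, and it is measured before the drug is given. An 80% control rate cannot arise among officers who were all selected for having TTS, and no drug effect can appear in a measurement that precedes the drug.

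Two things are at stake. First, the protocol gives readers an assurance of high power for a secondary comparison that the design rules out. Second, one term serves as entry criterion, outcome label and covariate. That leaves room for a pre-dose quantity to be tabulated by arm and read as efficacy, when any difference in it could only be chance imbalance at randomisation. The secondary tests carry no multiplicity adjustment, so nothing in the plan would temper such a result.

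**Working it through.** **Inputs** (Protocol 12.3, secondary outcomes): n = 63 per arm, p1 = 0.80, p2 = 0.48, one-sided alpha = 0.0235, stated power 96.1%. From Protocol 3.1b, 4.0, 5.2 and 9.0 and SAP 2.5: every randomised officer has TTS, identified before the dose.

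**Step 1. Reproduce the stated figure.** Pooled normal approximation:

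power = Φ{[(p1 − p2) − z·√(2p̄(1 − p̄)/n)] / √([p1(1 − p1) + p2(1 − p2)]/n)}

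with p̄ = (0.80 + 0.48)/2 = 0.64 and z = 1.986.

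- Null standard error: √(2 × 0.64 × 0.36/63) = 0.0855.
- Alternative standard error: √((0.1600 + 0.2496)/63) = 0.0806.
- (0.32 − 1.986 × 0.0855)/0.0806 = 1.86, so power = 96.9%.

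Other methods:

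| Method | n per arm | Rates | One-sided alpha | Power |
|---|---|---|---|---|
| Exact Fisher, full enumeration | 63 | 80% vs 48% | 0.0235 | 95.5% |
| Normal with continuity correction | 63 | 80% vs 48% | 0.0235 | 95.2% |
| Normal with continuity correction | 66 | 80% vs 48% | 0.0235 | 96.1% |
| Exact Fisher | 63 | 81% vs 48.6% | 0.0235 | 96.1% |

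The stated 96.1% is reproduced to within about one point. Which method produced it cannot be told from the documents, and it does not matter here.

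**Step 2. Apply the trial's own entry rule.** With p1 = p2 = 1, the table is 63/63 against 63/63 (or 66/66 against 66/66). The difference is 0, the one-sided Fisher p-value is 1.0 and the probability of rejection is 0.

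**Step 3. See where the 80% fits.** Protocol 12.4 uses the rate before randomisation: 60 × 0.80 = 48 officers qualify per year. Protocol 12.3 uses it after randomisation, as the control-arm rate. Both cannot be right, because the officers without TTS have already left. Only the screening-yield use fits the design.

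**Step 4. Compare with the main sample size.** The primary calculation in Protocol 12.3 uses 66 per arm and one-sided alpha 0.025. The TTS paragraph uses 63 and 0.0235 and explains neither. A 5% loss from 66 would leave 66 × 0.95 = 62.7, but no text makes that link.

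**Step 5. Check for a later TTS measurement.** The calendar has no audiogram at Visit 4. The only audiogram scheduled after the dosing visit is at Visit 5, day 30, where a shift of at least 10 dB at 2–6 kHz is the plan's definition of PTS.

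**Step 6. Check the DPOAE timing.** Protocol 4.0 names no visit. The note under Protocol 3.2 describes DPOAE as a secondary measure of TTS. SAP 3.3 places recordings at baseline, 5–10 minutes after shooting and 30 days. Recording takes about 20 minutes (Protocol 5.1), and no text says whether the Visit 3 recording comes before or after the dose.

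**The case against.** The strongest reply is that little turns on this. The SAP carries no TTS power statement and no TTS outcome in section 3.3, so what remains is a stray protocol paragraph and a loose label. That is largely fair, and it limits several stronger readings that a reader might draw.

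- **That the plan will test post-shooting TTS as efficacy.** The documents do not clearly say so. In Protocol 12.2.2 and SAP 7.1.2 the label stands in a list that ends with the 30-day time point. The outcomes are called continuous, and the model adjusts for post-shooting TTS, which would be degenerate if that were also the outcome. A 30-day shift is the natural reading. SAP Tables 14.2.1.7 and 14.2.1.8 already show audiogram change from baseline.
- **That TTS is constant in every sense.** Only the binary criterion is. Its size in dB varies between officers and can describe baseline balance or serve as a covariate.
- **That the paragraph really means TTS persisting at day 30.** It does not mention day 30. The plan's assumption for a shift at that visit is 50%, not 80%; Protocol 12.3 says of the 50%: "This is the proportion of PTS positive we expect to observe in the placebo group". No power figure for a day-30 TTS rate can be attributed to the plan.
- **That the Visit 3 DPOAE is known to be pre-dose, or that the Protocol 4.0 rate must move to Visit 5.** A 5–10 minute recording suggests a pre-dose start, but the order is not stated. SAP 3.3 already includes the 30-day DPOAE change, and the role of the early recording is the sponsor's choice of endpoint.

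None of this rescues the power claim, which is explicit and concerns the proportion of subjects with TTS in each arm.

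**Conclusion.** The power statement is wrong as written and should be corrected. For the binary TTS rate the design gives 0% power against the stated 96.1%. The cause is the choice of endpoint, not a calculation error. This rests on the entry rule and dosing order being followed; an officer randomised in error without TTS would be an exception, but that status would still precede the dose.

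The label in Protocol 12.2.2 and SAP 7.1.2 is an ambiguity to remove, not evidence of a planned invalid test. The DPOAE item is a gap in stated timing; the documents do not establish that the recording precedes the dose. The primary endpoint, the total of 132 subjects and the interim futility rule do not depend on any of this.

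**What to change.** 1. **Protocol 12.3:** delete the TTS power paragraph. This also removes the unexplained 63 per arm and alpha 0.0235, and brings the protocol into line with SAP 2.7.
2. **Protocol 12.2.2 and SAP 7.1.2:** replace Audiometric TTS as an outcome with the average audiogram threshold shift from baseline to 30 days, using the shift measure already in the Protocol 12.2.2 list of measurements. Add the same outcome to SAP 3.3. Keep average post-shooting TTS as a covariate only.
3. **Protocol 4.0, DPOAE outcome:** name the visit, and state whether the Visit 3 recording is made before or after the dose. Reconcile this with the note under Protocol 3.2 and with SAP 3.3. If the recording is pre-dose, state that it is not read as efficacy.

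The cost is an amendment to both documents. Items 2 and 3 clarify secondary endpoints, so they need the sponsor's agreement and should be settled before any unblinded results are seen. The audiogram and DPOAE data are already scheduled at Visits 2, 3 and 5. No visit, sample size or primary analysis changes.
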